### **5.1 Days to First Opioid Use**

The days to first opioid use will be tabulated based on the data collected on the TLFB where only illicit use is recorded. The days to first opioid use will begin being assessed on Day 0 where Day 0 is defined as the day of discharge into the community. An opioid use day is defined as use of any of the opioids reported on the TLFB including Buprenorphine, Opioid analgesics, Methadone, or Heroin. The first instance of use by self-report is defined as the first opioid use day.

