3.0 STUDY SCHEMA

4.0 INTRODUCTION

4.1 Background and Significance to the Field

For opioid use disorder patients in the U.S. and most of the rest of the world, detoxification or detoxification followed by short-term residential treatment, with the goal of achieving long-term abstinence from opioid misuse is a mainstay of treatment. Although it is widely believed that many patients treated in this way will rapidly relapse to opioid misuse – leading to a costly and ineffectual cycle of readmission for repeated detoxifications – there is scant data on opioid use outcomes following discharge from these programs. Searches of PubMed, NIH Reporter, and ClinicalTrials.gov for “clinical outcomes following opioid detoxification” and the like, mostly

reveal studies focused on detoxification methods, medication schedules, withdrawal symptomatology, tolerability and the proportion of patients completing detoxification.¹⁻⁶ Three studies,⁷⁻⁹ two of them from Europe, focused on subsequent outcomes (e.g., use, misuse, relapse) after patients completed detoxification. Gossop et al⁷ followed eighty patients discharged from 21-day methadone withdrawal programs at two United Kingdom hospitals between 1984 and 1986. Seventy-one percent used opioids within the first six weeks of discharge, and 81% used opioids at some point during the six-month follow-up, though at the six-month endpoint 51% were opioid-free. Broers et al⁸ followed 73 patients discharged from a Geneva, Switzerland 15-day (average) methadone tapering program between 1994 and 1995. Sixty-five percent were using drugs again (half of them regularly) within the first four weeks. At the six-month endpoint half of the population was physically dependent again. Chutuape et al⁹ followed 113 patients discharged from a 3-day medical (mostly clonidine) detoxification program in Baltimore, Maryland between May and November 1996. At the one-, three- and six-month post-discharge assessments, 25-36% reported almost daily use, 21-30% reported no use, and the remainder reported occasional use. Overall, the mean number of days of heroin use decreased from 28 days (in the month prior to admission) to 11-14 days. In addition, several studies, most of them randomized trials of buprenorphine detoxification, collected limited datasets on post-detoxification outcomes which were disappointing (only 3-47% self-reporting abstinence, and only 7-31% producing negative urine drug screens over one- to three-month follow up periods).¹⁰⁻²⁰

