13.1.1 Outcomes

We will collect the same drug use measures as are collected in CTN-0051. Outcomes are (1) days to first use and days to regular use (from TLFB), (2) number of days of use during the first eight weeks (or parts thereof, e.g., first week, first 4 weeks, etc.) post-discharge into the community (from TLFB), and (3) number of positive, negative and missing UDSs at weeks 1, 4 and 8. The days to first opioid use will also be assessed by self-report (TLFB) and calculated starting at the date of discharge to the community. The date of discharge to the community will be defined as Day 0. Overdoses and deaths will also be tracked (from safety reporting).

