### **5.2 Days to Regular Opioid Use**

The number of days to regular use will be tabulated based on the data collected on TLFB. The days to regular use will start on Day 0 where Day 0 is defined as the day of discharge into the community. An opioid use day is defined as use of any of the opioids reported on the TLFB including Buprenorphine, Opioid analgesics, Methadone, or Heroin. The first instance of seven consecutive days of use by self-report will define the participant as a regular user. The first day of the seven consecutive days is defined as the day to regular use.

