### **5.4 Days of Opioid Use**

The days of opioid use will be tabulated based on the data collected on the TLFB. An opioid use day is defined as use of any of the opioids reported on the TLFB including Buprenorphine, Opioid analgesics, Methadone, or Heroin.

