## **7.0 SAFETY ANALYSES**

Since this is an observational study with no intervention, no formal safety analysis is planned. Overdoses and deaths will be tracked from the safety event reporting.

[figure not shown]

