**Table 17: Summary of Days of Opioid Use by Type of Treatment Received Post-Discharge**

	Treatment Type Received Post-Discharge		
	Medication-assisted Treatment	No Medication-assisted Treatment	Total
Number of Participants			
Days of Opioid Use  up to Week 1			
N			
Mean			
SD			
Median			
Min			
Max			
Subjects Abstinent up to Week 1 N(%)			
Number of Imputed Days Per Subject (up to Week 1)			
N			
Mean			
SD			
Median			
Min			
Max			
Days of Opioid Use  up to Week 4			
N			
Mean			
SD			
Median			
Min			
Max			
Subjects Abstinent up to Week 4 N(%)			
Number of Imputed Days Per Subject (up to Week 4)			
N			
Mean			
SD			
Median			
Min			
Max			

 All missing self-reported use is imputed as positive.

 All missing self-reported use is imputed as positive.

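### Time to first use and abstinence draw on TLFB self-report only, so a participant who denies use on a complete TLFB but has an illicit-positive urine is classed as a non-user and abstinent

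*SAP*

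**What the plan says.** SAP 5.1 names the source for first use: "The days to first opioid use will be tabulated based on the data collected on the TLFB where only illicit use is recorded". It then fixes the event: "The first instance of use by self-report is defined as the first opioid use day". Protocol 13.1.1 agrees: "The days to first opioid use will also be assessed by self-report (TLFB) and calculated starting at the date of discharge to the community".

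The related outcomes use the same source. For regular use (SAP 5.2): "The first instance of seven consecutive days of use by self-report will define the participant as a regular user". For the count of use days (SAP 5.4): "The days of opioid use will be tabulated based on the data collected on the TLFB".

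Abstinence is listed in SAP 2.0 without a data source. It is tabulated only in the days-of-use tables (Tables 17-19), for example in the row "Subjects Abstinent up to Week 4 N". Its TLFB basis has to be inferred from that placement.

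Two other sources of evidence are collected:

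- UDS at Weeks 1, 4 and 8, with a rule in SAP 5.3 that sets aside positives explained by the treatment plan, and a Day 0 sample (Protocol 11.1). Results appear in Tables 14-16.
- Overdoses: "Overdoses and deaths will be tracked from the safety event reporting" (SAP 7.0). The Table 7 listing has columns for onset date and opioids involved.

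SAP 6.0 sets two rules for missing TLFB days. In time-to-event analyses, gaps between reports count as use, while days after drop-out are not imputed. In the count of use days, every missing day counts as use.

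**The concern.** The primary objective is to estimate opioid use rates after discharge. Neither document lets a positive urine or a recorded opioid overdose count as use, end abstinence or change censoring, and no table cross-classifies TLFB against UDS. The plan is therefore strict about absent evidence, since a gap in the TLFB counts as use, but makes no use of positive evidence that contradicts a completed TLFB.

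At stake are the any-use proportion and Kaplan-Meier curves (Tables 8-10, Figures 2-4) and the abstinence rows of Tables 17-19, overall and by subgroup.

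**Working it through.** **1. The plan's own figure for this outcome.** Table 1 (SAP 3.2.4) gives 82% power at N = 360, 60% users, HR 1.47, SD 0.5. Schoenfeld's formula, with the SD read as that of a binary covariate and alpha 0.05 two-sided:

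- events = 360 × 0.60 = 216
- √216 × 0.5 × ln(1.47) = 14.70 × 0.5 × 0.385 = 2.83
- power = Φ(2.83 − 1.96) = 80.8%

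This is within 2 points of the stated 82%. The point disputes no figure in the table; it borrows the 60-70% planning range as a baseline.

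**2. How the rules classify each case.**

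| Participant | Time to first use (Tables 8-10) | Abstinence (Tables 17-19) |
|---|---|---|
| Complete TLFB denying use; illicit-positive UDS | Any Opioid Use = No; censored | Abstinent |
| Gap between completed TLFB reports | Use on the missing days | Not abstinent |
| No use reported, then drops out | Censored as non-user | Not abstinent once missing days are imputed as use |
| No use reported, then dies of an opioid overdose before the next TLFB | Censored as non-user (death read as drop-out) | Not abstinent, for the same reason |

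The UDS conflict in both sets of tables is confined to the first row. The overdose problem (last row) affects only the time-to-event analysis.

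**3. Illustration of size.** Let p be any use by TLFB and q the share of self-reported non-users with contrary study evidence. The documents do not give q; 5-30% is an assumption. The formula also treats every self-reported non-user as having a complete TLFB. Revised any use = p + (1 − p) × q.

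| q | p = 60% | Reclassified of 360 | p = 70% | Reclassified of 360 |
|---|---|---|---|---|
| 5% | 62% | 7 | 71.5% | 5 |
| 10% | 64% | 14 | 73% | 11 |
| 20% | 68% | 29 | 76% | 22 |
| 30% | 72% | 43 | 79% | 32 |

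The shift is 2-12 points from 60% and 1.5-9 points from 70%.

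**4. Against sampling error.** The 95% half-width is 1.96 × √(p(1 − p)/N). At p = 70% it is 1.96 × √(0.21/360) = 4.7 points, or 5.2 points at N = 300 (the SAP's five sites × 60). At N = 360 the shift is thus 1.5/4.7 = 0.3 to 9/4.7 = 1.9 half-widths. It equals one half-width at q = 4.7/30, about 16%.

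**5. Power.** In the 60% case, the extra events move power at HR 1.47 from 80.8% to 82.1% (q = 5%) and 87.3% (q = 30%). The issue is the estimated rate, not power.

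**The case against.** Several objections have force.

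- **The UDS evidence is reported.** UDS is a separate listed outcome, tabulated by visit for the same three subgroup splits (Tables 14-16), and TLFB as the source for first use is a stated protocol choice. So it would be wrong to say the evidence is ignored. But separate marginal tables cannot show how many participants counted as abstinent had a positive urine.
- **Non-fatal overdoses are found by asking.** Staff ask about them at Weeks 1, 4 and 8, the same visits as the TLFB, so they are largely the same self-report. The overdose part matters mainly for deaths, and few participants are likely to be affected.
- **UDS is imperfect evidence of new use.** It does not date use. A Week 1 positive may reflect use before discharge or medication given on the unit. Treatment-plan status, which decides whether a positive is illicit, is asked only at visits. This supports a sensitivity analysis rather than a change of main definition.

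A reader might also infer three stronger conclusions that the documents do not support.

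- **That overdose deaths are counted as abstinent.** They are not in Tables 17-19, because every missing day counts as use there.
- **That reported use rates are too low overall.** The imputation rules push the other way, and abstinence in Tables 17-19 may even be too low, so the net direction is unknown.
- **That Protocol 4.1 demonstrates under-reporting,** where it cites "only 3-47% self-reporting abstinence, and only 7-31% producing negative urine drug screens". These are unpaired ranges pooled over several studies, and the second lies inside the first. They give no discordance rate.

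**Conclusion.** The point holds as a gap in definition. Among participants with a complete TLFB, leaving out an illicit-positive UDS can only understate any use and overstate abstinence. In the time-to-event analysis alone, death from an opioid overdose before the next TLFB is censored as non-use.

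The size is unknown. The ranges of 1.5-9 points (from 70%) and 2-12 points (from 60%) rest wholly on the assumed 5-30% discordance and on the plan's 60-70% use range. At the low end the shift is small beside sampling error; at the high end it exceeds it. The case is for measuring the discordance, not for asserting a large bias. Because the study is descriptive and the data are in hand, this is a cheap improvement rather than the repair of an error that invalidates the main analysis.

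**What to change.** Keep the TLFB definition as the main one and add the following.

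(a) **Abstinence.** State in SAP 2.0 that abstinence is TLFB-based. In Tables 17-19 add a row *abstinent, UDS-confirmed*: no reported use and no newly illicit-positive post-discharge UDS up to that visit, under the SAP 5.3 rule. The Day 0 sample serves only as the baseline, and a sample already positive at the previous test does not count. Show participants who report no use but lack a UDS in a separate row, *abstinent, UDS missing*; telephone assessments (Protocol 10.10) yield no urine, and these participants should not be labelled confirmed. A footnote should count those positive at every test from Day 0 on, since the rule leaves them as confirmed.

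(b) **Time to first use.** Add a sensitivity analysis in which a newly illicit-positive UDS with no reported use is an event in the interval since the previous visit. Treat it as interval-censored or date it at the visit, and state the rule for when the previous UDS is missing. An opioid-involved overdose is an event on its onset date.

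The cost is two table rows with a footnote, one sentence of definition and one sensitivity analysis, with no new data or procedures. The drawback is that some Week 1 positives may still be carry-over or unit medication, which is why this should stay a sensitivity analysis.

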### **5.2 Days to Regular Opioid Use**

The number of days to regular use will be tabulated based on the data collected on TLFB. The days to regular use will start on Day 0 where Day 0 is defined as the day of discharge into the community. An opioid use day is defined as use of any of the opioids reported on the TLFB including Buprenorphine, Opioid analgesics, Methadone, or Heroin. The first instance of seven consecutive days of use by self-report will define the participant as a regular user. The first day of the seven consecutive days is defined as the day to regular use.

### **5.3 Urine Drug Screen Results**

The urine drug screen (UDS) is used to assess whether the urine sample is positive for non-protocol opioids. Use for a urine sample is defined as a positive result for any of the following tests: Opiates (2000 ng), Oxycodone (OXY), Methadone (MTD), Opiates (300 ng) or Buprenorphine (BUP). UDS results are assessed at Weeks 1, 4, and 8. Illicit use only will be assessed. For example, if a subject is on a methadone treatment plan, UDS results positive for methadone will not be treated as positive UDSs.

### **5.4 Days of Opioid Use**

The days of opioid use will be tabulated based on the data collected on the TLFB. An opioid use day is defined as use of any of the opioids reported on the TLFB including Buprenorphine, Opioid analgesics, Methadone, or Heroin.

### **5.5 Analysis Methods**

For modeling the days to first opioid use and days to regular opioid use outcomes measures, a Cox regression model will be used after an assessment of the proportional hazards assumption. Should the key proportional hazards assumption be violated for a particular outcome and covariate, alternative models will be considered. The second set of outcomes relate to the number of days of opioid use. It is anticipated that the number of days of use will be non-normal, however we elect to analyze the data via a *t*-test which is fairly robust to misspecification of the underlying outcome distribution. Quantile regression may be used if modeling with multiple covariates is appropriate. For UDS-based outcomes, the dependent variable is binary (i.e., indicator of use or indicator of missingness) so univariate comparisons will be made using Pearson's  $\chi^2$  and any multivariate modeling will be implemented using logistic regression.

The second set of outcomes relate to the number of days of opioid use. It is anticipated that the number of days of use will be non-normal, however we elect to analyze the data via a *t*-test which is fairly robust to misspecification of the underlying outcome distribution. Quantile regression may be used if modeling with multiple covariates is appropriate. For UDS-based outcomes, the dependent variable is binary (i.e., indicator of use or indicator of missingness) so univariate comparisons will be made using Pearson's  $\chi^2$  and any multivariate modeling will be implemented using logistic regression.

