13.3 Statistical Methods for Primary and Secondary Outcomes

The primary objective of this study is to estimate opioid use rates, via various measures of use (Section 13.1.1), overall and separately for the sub-groups defined by use of medication-assisted treatment and type of treatment received at the enrolling site. Secondary exploratory analyses will involve modeling of opioid use as a function of certain independent predictors (see Section 13.2). For the primary objective all continuous variables (e.g., percent use days in the first week) will be summarized using the following descriptive statistics: n (non-missing sample size), mean, standard deviation, median, maximum and minimum. The frequency and percentages (based on the group-specific sample size) of observed levels will be reported for all categorical measures.

To evaluate secondary exploratory outcomes, two main sub-groups from the observational cohort are (1) participants who receive any medication-assisted treatment and (2) participants who do not receive medication-assisted treatment. All outcomes listed in Section 13.1.1 will be calculated separately for each of these subgroups of the observational cohort, as well as in the overall study sample. Program type, that is, short-term detoxification vs. short-term residential rehabilitation, will also define groups to be separately analyzed.

For modeling the days to first opioid use and days to regular opioid use outcomes measures, a Cox regression model will be used after an assessment of the proportional hazards assumption. Should the key proportional hazards assumption be violated for a particular outcome and covariate, alternative models will be considered. The second set of outcomes relate to the number of days of opioid use. It is anticipated that the number of days of use will be non-normal, however we elect to analyze the data via a *t*-test which is fairly robust to misspecification of the underlying outcome distribution. Quantile regression may be used if modeling with multiple covariates is appropriate. For UDS-based outcomes, the dependent variable is binary (i.e., indicator of use or indicator of missingness) so univariate comparisons will be made using Pearson's χ^2 and any multivariate modeling will be implemented using logistic regression.

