### **1.2 Study Design**

This is an observational study of participants with opioid use disorder leaving 5 of the detoxification and/or short-term residential units from which participants for CTN-0051 are recruited, but who are discharged to TAU in the community. Similar drug use measures but not identical are collected in this study as in CTN-0051. The goal is to estimate (1) days to first use and days to regular use, (2) number of days of use during the first four and eight weeks post-discharge to the community, and (3) number of positive, negative and missing UDSs at weeks 1, 4 and 8 post-discharge to the community.

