#### 3.2 Sample Size and Power Calculations

##### 3.2.1 Rationale for Sample Size and Statistical Power

No formal statistical hypothesis tests will be calculated for this study; therefore, there is neither sample size nor statistical power calculations. The study population is a convenience sample and it is anticipated that each participating site should be able to enroll approximately 60 participants for a total of approximately 360 participants. While the main objectives of this study are descriptive in nature, such as estimating the opioid use rate eight weeks after discharge to the community, it may be of interest to evaluate whether these opioid use outcomes are associated with certain covariates. Potential independent predictors of opioid use include: age, gender, race, ethnicity, use of medication-assisted treatment, and type of treatment received prior to discharge to the community.

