##### 3.2.2 Number of Sites

Five sites with inpatient detoxification programs and/or short-term residential treatment programs associated with CTN-0051 will recruit participants.

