##### 3.2.3 Projected Number of Participants per Site

Approximately 60 participants will be recruited at each of the approximately six sites.

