### 3.3 Software

All analyses will be performed utilizing SAS® version 9.3 or higher. All statistical tests will be conducted at the 5% Type I error rate (two-sided). When multiple tests are conducted, the chance of finding a significant difference in one of the tests, when in fact no difference exists, is greater than the stated Type I error rate. The investigators are aware of the multiple testing issues and will interpret results with caution and use confidence intervals where possible.

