**Table 4: Summary of Baseline Characteristics by CTP**

Characteristic	OV Maryhaven	FL Gateway Community Services	PA Tarzana Treatment Centers	NEC Stanley Street Treatment and Resource	GNV Bellevue Hospital Center	Total
Education completed						
Less than high school diploma						
High school graduate						
GED or equivalent						
Some college, no degree						
Associate's degree: occupational, technical, or vocational program						
Associate's degree: academic program						
Bachelor's degree						
Master's degree						
Professional school degree						
Doctoral degree						
Don't know						
Refused						
Marital status						
Married						
Widowed						
Divorced						
Separated						
Never married						
Living with partner						
Refused						
Don't know						
Employment						
Working now						
Only temporarily laid off, sick leave, or maternity leave						
Looking for work, unemployed						
Retired						
Disabled permanently or temporarily						
Keeping house						
Student						
Other						

Table 5: Summary of Subgroups of Interest by CTP						
Subgroups of Interest	OV Maryhaven	FL Gateway Community Services	PA Tarzana Treatment Centers	NEC Stanley Street Treatment and Resource	GNY Bellevue Hospital Center	Total
Treatment Type Received Post-Discharge						
Medication-assisted Treatment						
No Medication-assisted Treatment						
Length of Stay						
≤7 days						
8-20 days						
≥ 21 days						
Baseline Opioid Severity Level*						
Low Severity						
High Severity						
Baseline Opioid Severity Level/ Treatment Type Received Post-Discharge						
Low Severity/ Medication-assisted Treatment						
Low Severity/ No Medication-assisted Treatment						
High Severity/ Medication-assisted Treatment						
High Severity/ No Medication-assisted Treatment						
Baseline Opioid Severity Level*						
Low Severity/ ≤7 days						
Low Severity/ 8-20 days						
Low Severity/ ≥ 21 days						
High Severity/ ≤7 days						
High Severity/ 8-20 days						
High Severity/ ≥ 21 days						

\* To compute the opioid severity level, if the primary opioid of use in the last 7 days was not heroin or the route of administration is not IV-injection then that participant is defined as a low severity user. For IV heroin users where the quantity is not provided in bags but in dollars, bags are estimated as the dollar amount/10 rounded to the nearest integer.

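### No planned opioid-use comparison accounts for site in a five-program cohort, so the medication-assisted-treatment and length-of-stay contrasts may be confounded with site

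*SAP*

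**What the plan says.** **Sites.** SAP 3.2.2 states: "Five sites with inpatient detoxification programs and/or short-term residential treatment programs associated with CTN-0051 will recruit participants". SAP 1.2 also gives five, while SAP 3.2.3 keeps the protocol's count: "Approximately 60 participants will be recruited at each of the approximately six sites". SAP 3.2.1 calls the cohort a convenience sample.

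**Methods.** For days to first use and to regular use, SAP 5.5 states that "a Cox regression model will be used after an assessment of the proportional hazards assumption". Days of use are compared by t-test, with quantile regression as an option. For urine drug screens (UDS), Protocol 13.3 and SAP 5.5 agree that "univariate comparisons will be made using Pearson's" chi-square, with logistic regression for any multivariable model. No site covariate, stratum, random effect or cluster-robust variance is named.

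**Predictors.** SAP 3.2.1: "Potential independent predictors of opioid use include: age, gender, race, ethnicity, use of medication-assisted treatment", followed by the type of treatment before discharge. Protocol 13.2 has the same list. Site is not on it.

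**Tables and figures.** Site (CTP in the SAP's table shells) appears in Tables 1 to 7, among them "Table 5: Summary of Subgroups of Interest by CTP". Opioid-use Tables 8 to 19 and Figures 2 to 7 are split only by MAT, length of stay or baseline severity.

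**Program type.** SAP 2.3 defines program type by length of stay, in three bands: up to 7, 8 to 20, and 21 or more days.

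**The concern.** A MAT contrast pooled over sites mixes two comparisons: patients with and without MAT at the same site, and sites that link many patients to MAT against sites that link few. If opioid use after discharge also differs between those sites, the pooled contrast shows a MAT association even when none exists within any site.

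Length of stay is more exposed. The SAP uses it to stand for program type, and the participating sites run detoxification units, residential units, or both. Length of stay may therefore be largely set by which site a participant attended, so that a crude comparison of the three bands would in part compare facilities.

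These contrasts are not marginal output. SAP 5.0 places subgroup estimates within the primary objective, and SAP 3.3 sets a two-sided 5% level for all tests, so readers will see subgroup results side by side, some with p-values.

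**Working it through.** **1. The plan's own figure.** SAP Table 1 gives 82% power at N = 360, hazard ratio (HR) 1.47 and 60% with an event, with a standard deviation of 0.5, which fits a 50:50 binary covariate. The usual Cox formula is power = Φ(√(N × p) × SD × ln HR − 1.96).

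√(360 × 0.60) × 0.5 = √54 = 7.348; ln 1.47 = 0.385; 7.348 × 0.385 − 1.96 = 0.87; power = 80.8%.

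The row with 70% events and HR 1.45 gives 83.9% against the stated 84%. The detectable HR at exactly 80% power with 60% events is 1.46, as the text says. These figures therefore reproduce without any site term.

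**2. Two-group illustration (all inputs assumed).** Three sites, n = 180: 20% on MAT, 75% using by week 8. Two sites, n = 120: 60% on MAT, 55% using. There is no MAT effect within any site.

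- MAT: 36 + 72 = 108 people; (36 × 0.75 + 72 × 0.55)/108 = 66.6/108 = 61.7% using.
- No MAT: 144 + 48 = 192 people; (144 × 0.75 + 48 × 0.55)/192 = 134.4/192 = 70.0% using.
- Crude odds ratio, MAT versus none: (66.6/41.4)/(134.4/57.6) = 1.609/2.333 = 0.69. The within-site value is 1.00.

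**3. Range over assumed mixes.** Five equal sites, mean use 65%, no within-site effect, higher MAT share at the sites with less use; 20,000 simulated studies at N = 300 and at N = 360. The test columns give the share of studies significant at 5%.

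| MAT share across sites | Use across sites | OR, MAT vs none | Same, none vs MAT | Pearson chi-square | Site-stratified Mantel-Haenszel |
|---|---|---|---|---|---|
| 50% at all | any of the ranges run | 1.00 | 1.00 | about 5% | about 5% |
| 40–60% | 55–75% | 0.92 | 1.09 | about 7% | about 5% |
| 30–70% | 55–75% | 0.84 | 1.19 | about 12% | about 5% |
| 30–70% | 45–85% | 0.70 | 1.42 | 31–35% | about 5% |
| 10–90% | 45–85% | 0.49 | 2.04 | 84–90% | about 5% |

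If MAT were instead more common at the sites with more use, the association would point the other way.

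**4. Price of adjustment.** If site explains a share R² of the variance of the predictor, the events in step 1 are multiplied by (1 − R²). The documents give no R², so the values are assumed. N = 360, 60% events:

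| R² | Power at HR 1.47 | HR detectable at 80% power |
|---|---|---|
| 0 | 80.8% | 1.46 |
| 0.1 | 76.6% | 1.50 |
| 0.2 | 71.6% | 1.53 |
| 0.3 | 65.9% | 1.58 |
| 0.5 | 51.7% | 1.72 |

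A 30–70% spread in MAT share over five equal sites corresponds to R² = 0.02/0.25 = 0.08, and a 10–90% spread to 0.08/0.25 = 0.32.

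**The case against.** **The comparisons are exploratory and the predictor list is open.** SAP 5.5.1 disclaims formal testing, SAP 3.3 promises cautious interpretation, and the list of predictors is introduced as potential and not closed. This stands in part: site is unspecified, not excluded, and no passage claims a causal MAT effect. But the t-test, the chi-square test and the Kaplan-Meier curves carry no covariates, so an open list does not help them.

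**A subgroup rate is a valid description whatever the site mix.** True, and the crude summaries should stay. The difficulty begins when two such rates are compared.

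**The illustrated bias is modest.** With the expected counts in step 2, the standard error of the log odds ratio is √(1/66.6 + 1/41.4 + 1/134.4 + 1/57.6) = 0.25, so the 95% interval around 0.69 is about 0.42 to 1.13. That assumed case would not reach significance at its expected value. This is fair.

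**Adjusting length of stay for site may remove the contrast being described.** This stands, and is why both versions are needed.

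A reader might also infer four stronger things that the documents do not support:

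- *That the contrasts are confounded.* Both the exposure mix and opioid use must differ between sites. Table 5 is an empty shell, and no data on either are given.
- *That the SAP expects imbalance because Table 5 is by site.* Tables 1 to 7 are all by site, including screen failures and marital status. This is routine reporting, and Table 5 is the display that would reveal an imbalance.
- *That no outcome is shown by site.* Overdoses and deaths, tracked under Protocol 9.1, are reported by site in Tables 6 and 7.
- *That clustering makes the pooled rates look too precise.* No intraclass correlation is given. The sites are a fixed convenience set, and the primary summaries in SAP 5.0 list no intervals. Site stratification would not change the overall rates in any case.

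**Conclusion.** The omission is plain from the text: no planned opioid-use model or test includes site, and no opioid-use table or figure is shown by site, in a cohort from five programs. The MAT and length-of-stay contrasts may therefore be confounded with site, with no planned adjustment.

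The size cannot be known from the documents. Under assumed mixes with no within-site effect, the crude odds ratio (MAT versus none) runs from 1.00 with an equal MAT share to about 0.70 with marked site differences, and to 0.49 in the most extreme mix tried. The site-stratified test holds its 5% level throughout. For length of stay the risk is more plausible on the SAP's own definition, but no figure can be attached.

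This is a cheap improvement to an exploratory part of the plan. It does not make the subgroup descriptions wrong, and adjusting for site would not by itself make a MAT contrast causal.

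**What to change.** In SAP 5.5, before the outcome data are analysed:

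- Keep the crude summaries, curves and tests, labelled as descriptive.
- Beside them, report Cox models stratified by site, site as a fixed effect in the logistic and quantile models, a Cochran-Mantel-Haenszel test beside Pearson's chi-square, and a site-adjusted linear model beside the t-test. Five sites suit strata or fixed effects; they are too few for a reliable random-effect or cluster-robust variance.
- Add one table of the opioid-use outcomes by site.
- For length of stay, show crude and site-adjusted results together. Where Table 5 shows that it largely coincides with site, state that the two cannot be separated.
- Reconcile the site count (five in SAP 1.2 and 3.2.2, about six in 3.2.3), since it sets the number of strata.

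Site is already recorded, so the cost is a few lines of text and code. The downside is wider intervals and lower power for predictors that vary mainly between sites: at an assumed R² of 0.3, power at HR 1.47 falls from 80.8% to 65.9%.
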